The current plan is for the study to be conducted at the Children's Day Unit (CDU) at NYPSI and the Irving Institute for Clinical and Translational Research at CUMC. The CDU is an outpatient clinic and a research day treatment program that provides services for the psychiatric and educational needs of children and adolescents participating in research protocols at NYSPI. Most of the children have either failed or not completely responded to first line treatments for mood, OCD, or other anxiety disorders. School services are provided by PS186X, a New York City public school located on the unit during the academic year from September through June. In addition, during the 6 week summer program in July and August, the CDU provides educational tutoring. This unit provides continued clinical care for children and adolescents after their participation in an IRB approved protocol at no cost. Led by [name], the staff consists of a research medical director, [name], a research nurse, a social worker, psychologists, and trainees. Although this protocol is primarily conducted as an outpatient study, we reserve the opportunity to offer admission to 4 Center (the 4th floor inpatient unit) for those adolescents in need of a higher level of care. If an adolescent requires additional support, the adolescent may be admitted to the CDU partial day program that runs Monday through Friday from 8:30 AM to 3:30 PM where the adolescent can be closely monitored, receive educational credit, and additional supportive services.

Screening:

Upon consenting, participants will complete all screening procedures at the CDU. Screening may last from 1 to 6 weeks to allow sufficient time to obtain thorough medical and psychiatric history to ensure the patient's safety and eligibility/ineligibility in the study. Screening procedures include:

- *Diagnostic Assessment:* Anxiety Disorders Interview Schedule Child/Parent version (The child version will be administered to all participants. The parent version will be administered to parents of all participants ages 14-17 and to parents of participants ages 18-22 with their permission).
- *Efficacy Assessments:* Children's Yale-Brown Obsessive Compulsive Scale (CYBOCS), Children's Depression Rating Scale-Revised (CDRS-R).

Note: Diagnostic and Efficacy Assessments will be be administered by one of the study's Independent Evaluators ([name], [name], [name] or [name]).

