In order to be eligible for this study, participants must be off all psychotropic medications aside from SRIs and other types of drugs likely to interact with glutamate for at least 14 days prior to starting the study. After consent is signed, if a medication washout is necessary, it can either be performed by a psychiatrist at the Pediatric Anxiety & Mood Research Clinic (PAMRC) or by the participant's own physician. During this washout period, patients will be monitored at least weekly in person and by phone more frequently if needed. Weekly assessments during the washout period will include the Clinical Global Impressions Scale (CGI-S). If a patient's score on the Global Improvement section of the CGI is a 6 ("much worse") or 7 ("very much worse") during the washout period, the clinician will take the patient off the protocol washout and initiate the 3-month open clinical treatment offered to all patients at the end of the study. Patients may independently elect to withdraw from standardized treatment at any time for any reason, independent of their CGI Global Improvement score. Physical exam, vital signs and adverse events will also be carefully assessed during the washout period.

Day 1: Baseline Evaluation & Ketamine Infusion

Baseline Evaluation

After completing the screening procedures and medication washout if applicable, participants will proceed to the baseline evaluation. Baseline evaluation procedures include:

- *Efficacy Assessments:* Children's Yale-Brown Obsessive Compulsive Scale (CYBOCS), Children's Depression Rating Scale-Revised (CDRS-R), Young Mania Rating Scale (YMRS), Clinician Administered Dissociative States Scale (CADSS), Brief Psychiatric Rating Scale (BPRS), OCD Visual Analogue Scale (OCD-VAS), Yale-Brown Obsessive Compulsive Challenge Scale (YBOCCS), Child Obsessive-Compulsive Impact Scale-Revised (COIS-R)
- *Feasibility and Safety Assessment*: Columbia-Suicide Severity Rating Scale (C-SSRS)
- Clinical Global Impressions Scale (CGI)
- Medical Assessment: Vital Signs and Pregnancy Test (urine) for female participants

Test Day Procedures

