
Upon completion of the 14-day study period, participants will be offered an additional 3 months of open treatment for OCD (medication management and/or CBT) as clinically indicated based on their treatment

history. If a participant has not yet had a trial of Clomipramine, we will offer that medication to the participant following the 14 day period. In the event that they prefer to be treated elsewhere, they will also be provided with referrals to community providers. With their permission, all participants will be assessed at a 3-month follow-up visit. Participants will be asked to return to the CDU to complete the following assessments: Children's Yale-Brown Obsessive Compulsive Scale (CYBOCS), Clinical Global Impressions Scale (CGI), OCD Visual Analogue Scale (OCD-VAS), Yale-Brown Obsessive Compulsive Challenge Scale (YBOCCS), and vital signs. This will be pilot data to help us evaluate patient satisfaction, ongoing safety, and maintenance of response.

You can upload charts or diagrams if any

Criteria for Early Discontinuation

Criteria for Early Discontinuation

Participants are free to withdraw from the study at any time for any reason. Study doctors are to discontinue participants from the study if participants:

- Request early discontinuation or withdraw consent.
- Experience a serious or intolerable adverse event that prevents the participant from continuing.
- In the study clinician's opinion are evaluated to be much worse (CGI-I score of 6) for two consecutive visits. If the participant begins to show clinical deterioration during the 14-day treatment phase and further continuation under such circumstances would be detrimental to the participant, a referral will be made for a clinical evaluation by an independent evaluator to determine whether the participant should be withdrawn from the study.
- In the study clinician's opinion are experiencing clinically significant deterioration in a comorbid condition such as major depression. For example, if a participant became suicidal or their symptoms of depression increased such that the depressive symptoms were much or very much worse relative to baseline and the CDRS is no longer <60, they would be discontinued from the study.
- Are lost to follow-up.
- Encounter other conditions (such as administrative issues or pregnancy).

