DSM-IV OCPD Assessment: This is a semi-structured interview that assesses for symptoms of Obsessive Compulsive Personality Disorder.

Please attach copies, unless standard instruments are used

Off label and investigational use of drugs/devices

Choose from the following that will be applicable to your study
✓ Drug
Select the number of drugs used in this study
1

Drug #1

Name of the drug Ketamine Manufacturer and other information Ketamine Approval Status No IND is required Choose one of the following options FDA conditions are met (see 'Rules') Explain We completed the IND Decision Worksheet and it appears that we do not need to apply for an IND exception. The IND Decision Worksheet was previously uploaded for review.

Research Related Delay to Treatment

Will research procedures result in a delay to treatment?

Yes

Maximum duration of delay to any treatment

For enrolled participants that do not require a medication washout, there will be no delay to receiving treatment. For enrolled participants that require a medication washout, the maximum delay in initiating study treatment will be two weeks.

Maximum duration of delay to standard care or treatment of known efficacy

For all enrolled participants, the maximum delay to standard care or treatment of known efficacy will be 14 days.

Treatment to be provided at the end of the study

Upon completion of the acute 14-day treatment period, participants will be offered three additional months of open treatment for OCD (medication management and/or CBT) at no cost. This treatment will be offered to all participants regardless of response during the acute study treatment period. For participants requiring continued OCD treatment following this three-month follow-up period, the research staff will refer the patient to his or her previous providers or will assist the participant and his/her family in identifying new treatment providers.

Clinical Treatment Alternatives

Clinical treatment alternatives

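### The 14-day maximum delay to standard care leaves out the washout (27 to 28 days for a fully washed-out completer); separately, one rescue step carries two nitroglycerin doses

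*Protocol*

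**What the plan says.** **Delay.** Research Related Delay to Treatment (Protocol) has two entries. On delay to any treatment, participants without a washout are said to have none; for the others, "For enrolled participants that require a medication washout, the maximum delay in initiating study treatment will be two weeks". On delay to standard care, the entry reads "For all enrolled participants, the maximum delay to standard care or treatment of known efficacy will be 14 days".

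Standard care comes after the post-infusion phase. Treatment to be provided at the end of the study says "Upon completion of the acute 14-day treatment period, participants will be offered three additional months of open treatment for OCD", and Follow-up Treatment says the same: "Upon completion of the 14-day study period, participants will be offered an additional 3 months of open treatment for OCD".

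The Washout section places a needed washout inside the study ("After consent is signed, if a medication washout is necessary") and requires participants to be off psychotropics other than SRIs and off "drugs likely to interact with glutamate for at least 14 days prior to starting the study". Baseline evaluation and infusion follow. If a participant worsens markedly on the CGI during washout, "the clinician will take the patient off the protocol washout and initiate the 3-month open clinical treatment". The Screening section adds: "Screening may last from 1 to 6 weeks".

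**Nitroglycerin (separate item).** Safety and Termination of Ketamine Infusion appears twice, under Study Procedures and under Risks. Both versions describe the same step for very high blood pressure, with the same clonidine range. The single sublingual nitroglycerin dose is 0.4 mg in the first and 0.3 mg in the second.

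**The concern.** For a participant without a washout, the 14 days can only be the post-infusion phase. For a participant with a washout, the same section counts up to two further weeks as delay, yet the total stated for everyone stays at 14 days.

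This is the figure offered to the review board for weighing time without standard care, in a sample that includes minors. Item 3 of the Risks section says that being off medication may worsen OCD and depression and carries a suicide risk. It also treats the washout as a delay in treatment, because a participant who cannot tolerate it is to be withdrawn and given known OCD drugs. An understated maximum therefore bears on the weighing of risk, and on consent if the forms repeat it.

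The nitroglycerin discrepancy has nothing to do with the delay. It matters because one rescue step should carry one dose.

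**Working it through.** **Inputs**
- Stated maximum delay to standard care: 14 days (Research Related Delay to Treatment).
- Delay to infusion: 0 days without washout, up to 14 days with washout (same section).
- Infusion to the offer of open treatment: 14 days if the final visit is counted as 14 days post-infusion (Day 2 – 14 section), or 13 days if the infusion day is Day 1 (Day 1 heading).
- Screening and any drug taper are left out throughout.

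**Formula:** delay = washout days served after consent + days from infusion to open treatment.

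**The plan's own figure:** 0 + 14 = 14 (or 0 + 13 = 13). The stated maximum is reproduced only with no washout.

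| Case | Calculation | Days | Above 14? |
|---|---|---|---|
| No washout, phase completed | 0 + 13 or 14 | 13–14 | no |
| Full washout, phase completed | 14 + 13 or 14 | 27–28 | yes |
| Full washout, CGI exit at day 7 | 14 + 6 or 7 | 20–21 | yes |
| Full washout, CGI exit at day 3 or 4 | 14 + 2 to 4 | 16–18 | yes |
| Exit during a two-week washout | at most 14 | ≤14 | no |
| Partial washout, 7 days left at consent | 7 + 13 or 14 | 20–21 | yes |

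Ratios for the full-washout completer: 27/14 = 1.93 and 28/14 = 2.0.

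For a partial washout with r days left at consent, the total is r + 13 to r + 14. It passes 14 once r is at least 1 on the 14-day count, or at least 2 on the 13-day count.

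**Query, not part of the 27 to 28 days.** Inclusion criterion 7 asks for 1 month off neuroleptics and 6 weeks off fluoxetine. The Washout section, Risks item 3 and the delay section mention only 14 days or two weeks. Criterion 7 does not say whether the longer periods may be served after consent. If they may, the two-week cap on delay to study treatment fails too. The totals would be 41 to 45 days for neuroleptics (28 to 31 days assumed for 1 month, plus 13 or 14) and 55 to 56 days for fluoxetine (42 plus 13 or 14). Criterion 7 also excepts SRIs and then lists fluoxetine, so its status is unclear.

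**Nitroglycerin:** 0.4 − 0.3 = 0.1 mg between two accounts of the same step.

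**The case against.** **The start of the count is undefined.** Screening follows consent as well, and nothing bars a two-week washout from running inside the screening window. Counted from consent with screening included, even a participant without washout would wait 7 to 42 days plus 13 or 14, that is 20 to 56 days. Counted from infusion, 14 days is right for everyone. This is fair, and the fix must settle the clock first. It does not rescue the sentence, which names no starting point, covers all enrolled participants, and stands beside an entry that counts washout as delay for participants it calls enrolled.

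**Standard care is not simply withheld.** SRIs are first-line according to Clinical Treatment Alternatives and may continue, and participants have already failed an SRI trial. For those on a stable SRI the delay concerns only new or additional treatment. That limits the harm. Even so, some participants will be medication-free, and exclusion criterion 10 rules out planning to start CBT during the study.

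**Early exits exist.** They do, and participants may withdraw at any time. The early-exit rows above are softer than the main figure. The day 3 or 4 visit is optional, and the single-visit CGI rule there and at day 7 differs from Criteria for Early Discontinuation, which asks for two consecutive visits. None of this changes the maximum for a completer.

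**The components were disclosed.** The two-week washout delay, the 14-day figure and the timing of open treatment stand close together, so a reader could add them. The stated total is still about half their sum.

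**Practical effect is small.** The number washed out is not given and may be zero, and the amended SAP (8.2) refers to study completion. This bears on urgency, not on whether the figure is right.

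**Conclusion.** The 14-day maximum is wrong as written for all enrolled participants. For a full two-week washout after consent and a completed phase, the Protocol's own figures give 27 to 28 days, 1.9 to 2.0 times the stated value. This assumes that washout counts as delay, as the same section and Risks item 3 treat it, and it leaves out screening and taper. Participants without washout, or who leave during a two-week washout, stay within 14 days.

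Reach is limited: 0 to 5 of the 5 enrolled at the Protocol's report. What families were told cannot be judged, because the consent forms are not available for review. Endpoints, sample size and analysis are unaffected.

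The nitroglycerin contradiction is confirmed as a separate item. Which dose, or which washout period, is right is not a matter for this review.

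**What to change.** 1. State when the count starts, and whether screening and taper are included.
2. On that basis, give the maximum delay to standard care separately: 14 days without washout and, with washout, the longest in-study washout kept plus 14 days. Say that early exits shorten it and that, for participants on a stable SRI, it concerns new or additional treatment.
3. Reconcile inclusion criterion 7, the Washout section, Risks item 3 and the delay section. Cover whether the neuroleptic and fluoxetine periods may be served after consent and whether fluoxetine falls under the SRI exception.
4. Check the consent and assent forms for the 14-day figure.
5. Separately, the sponsor and responsible clinicians must reconcile the two nitroglycerin doses.

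The cost is wording only, plus a longer and less favourable stated maximum for washed-out participants. If treatment is finished, correct the record and keep both errors out of the larger randomized trial that the Lay Summary foresees.

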Upload the entire grant application(s) Upload copy(ies) of unbolded Consent Form(s) OCD Ketamine_Young Adult Consent Form UNBOLDED 8.30.17.pdf OCD Ketamine Parent of Young Adult Consent Form UNBOLDED 8.30.17.pdf OCD Ketamine Parent Consent Form UNBOLDED 8.30.2017.pdf Upload copy(ies) of bolded Consent Form(s) Upload copy(ies) of unbolded Assent Form(s) OCD Ketamine Adolescent Assent Form UNBOLDED 8.30.2017.pdf Upload copy(ies) of bolded Assent Form(s) Upload copy(ies) of the HIPAA form HIPAA Child Authorization 8.30.17.pdf HIPAA Adult Authorization 8.30.17.pdf Upload any additional documents that may be related to this study IE Assessment of OCPD.pdf OCD Ketamine Study Flowchart for PSF Updated 11.30.15.pdf OCD Phone Screen #7023 Updated 12.22.16.pdf IRB7023 OCD Ketamine Recruitment Brochure Updated 8.15.17.pdf IRB7023 OCD Ketamine Recruitment Flyer Updated 12.14.17.pdf IRB7023 OCD Ketamine Recruitment Short Study Blurb Updated 12.21.17.pdf IRB7023 OCD Ketamine Recruitment Long Study Blurb Updated 12.21.17.pdf

1 INTRODUCTION

We will evaluate the feasibility/tolerability, and preliminary efficacy of ketamine, a medication that modulates glutamate in the brain, as a rapid treatment for OCD symptoms in adolescents with OCD. Our rationale for using ketamine is threefold. First, glutamatergic abnormalities in corticostriatal circuits may underlie OCD symptoms based on human imaging, genetic, and animal studies; striatal glutamatergic levels have been associated with OCD severity. Thus, medications that modulate glutamatergic neurotransmission (e.g., riluzole memantine, minocycline) may be effective. Second, riluzole and memantine have shown promise for OCD in case reports or open trials, but neither is FDA-approved for use in children; riluzole also has significant liabilities in terms of adverse events and cost. In contrast, ketamine is FDA-approved for anesthesia in children, adolescents and adults, and is routinely used at higher doses than proposed in this study. It is also used as adjunctive pain management for children and adolescents suffering from end stage medical illness. Third, we found in a small randomized controlled trial that unmedicated OCD adult patients had a near cessation of obsessional thoughts during an intravenous ketamine infusion; these effects were maintained in half of patients for up to one week (Rodriguez et al. 2013). These exciting findings lead to two questions: 1) is this type of study acceptable and feasible in youth; 2) are ketamine's effects similar in adolescents and young adults?

2 AIMS

We propose a pilot study to determine the acceptability, feasibility and potential efficacy of a single ketamine infusion in adolescents and young adults with OCD. Promising data will lead to a grant application to the National Institutes of Mental Health for a full scale randomized controlled trial.

Aim 1. To assess the feasibility/tolerability of using ketamine in adolescents with OCD Aim 2. To assess the effects of ketamine on OCD severity

3 PROCEDURES

We will recruit 5 adolescents and young adults (post-pubertal, ages 14-20) with OCD using similar criteria as in our prior ketamine study (Rodriguez et al. 2013) with the modification that participants have attempted at least one trial of a standard treatment (i.e., SRI and/or CBT). They will be free of medication and have at least moderate OCD severity (rating on Children's Yale-Brown Obsessive-Compulsive Scale [CY-BOCS] of at least 16) and near constant obsessions. After baseline assessment and evaluation, patients will receive a single infusion of intravenous ketamine 0.5 mg/kg. Obsessional severity will be evaluated at baseline, during the ketamine infusion and during post-infusion observation using the OCD-Visual Analogue Scale; OCD and depressive severity will be evaluated using the CY-BOCS (child version) and Children's Depression Rating Scale Revised at weekly intervals for 2 weeks after infusion.

4 ANALYSIS SET

This pilot study is a non-controlled clinical trial consisting of one group of participants. Participants will be adolescents and young adults with OCD who have failed at least one trial of standard treatment. All participants will receive an intravenous ketamine infusion.

5 OUTCOMES

- 6.1. Primary Outcomes
- i. Total number of screened participants
- ii. Total number completing
- 6.2. Secondary Outcomes
- i. CY-BOCS score at baseline, 1 week post-infusion, and 2 weeks post infusion
- ii. Children's Depression Rating Scale Revised at baseline, 1 week post-infusion, and 2 weeks post
- 6.3 Adverse Outcomes
- i. Adverse events will be assessed throughout the study period
- ii. Suicidality will be obtained with the Columbia-Suicide Severity Rating Scale (C-SSRS).

6 STATISTICAL ANALYSIS

Data will be analyzed using IBM SPSS. We will report descriptive statistics for all outcomes including mean and standard deviation.

8.1. Descriptive Statistics

For acceptability and feasibility, we will assess the number screened and the number completed by reporting total numbers and percentages.

8.2. Statistical Tests

For potential efficacy, continuous outcomes will be modeled as a function of time using mixedeffects regression, and the proportion of responders (CY-BOCS decrease $\geq 35\%$) and remitters (CY-BOCS ≤ 12) one and two weeks after the ketamine infusion will be computed. Differences in outcomes from baseline to 1 week post-infusion and 2 weeks post-infusion will be the independent variables. Study subjects will be considered as random effects and the proportion of responders and remitters as well as the difference of obsessional severity from baseline to postinfusion will be included as fixed effects. Sex and age will be considered as covariates. 95% confidence intervals, and p-values will be presented for each outcome variable and time point

7 MISSING VALUES

Mixed models provide adequate power without ad hoc imputations (Chakraborty & Gu, 2009). Thus, missing value will not be imputed.

1 INTRODUCTION

We will evaluate the feasibility/tolerability, and preliminary efficacy of ketamine, a medication that modulates glutamate in the brain, as a rapid treatment for OCD symptoms in adolescents with OCD. Our rationale for using ketamine is threefold. First, glutamatergic abnormalities in corticostriatal circuits may underlie OCD symptoms based on human imaging, genetic, and animal studies; striatal glutamatergic levels have been associated with OCD severity. Thus, medications that modulate glutamatergic neurotransmission (e.g., riluzole memantine, minocycline) may be effective. Second, riluzole and memantine have shown promise for OCD in case reports or open trials, but neither is FDA-approved for use in children; riluzole also has significant liabilities in terms of adverse events and cost. In contrast, ketamine is FDA-approved for anesthesia in children, adolescents and adults, and is routinely used at higher doses than proposed in this study. It is also used as adjunctive pain management for children and adolescents suffering from end stage medical illness. Third, we found in a small randomized controlled trial that unmedicated OCD adult patients had a near cessation of obsessional thoughts during an intravenous ketamine infusion; these effects were maintained in half of patients for up to one week (Rodriguez et al. 2013). These exciting findings lead to two questions: 1) is this type of study acceptable and feasible in youth; 2) are ketamine's effects similar in adolescents and young adults?

